5.6 Explanation for choice of comparator

Not applicable - no comparator will be used during this clinical investigation

5.7 Risk evaluation (Risk-to-Benefits rationale)

5.7.1 Potential Benefits

Hemanext has found that red cell degradation is O₂ dose dependent, and that if the O₂ concentration is reduced at the time of storage, it is possible to minimize degradation and optimize red cell quality³⁷. Hemanext designed a product and process to manage a broad range of % of SO₂ values in transfused RBC for oxygen-management. This product moves the entire broad % SO₂ distribution starting with a mean of 52% ranging from 10-90% SO₂ to mean of less than 20%. This is achieved on Day 0 and the product is designed to maintain this figure for 42 days of storage³⁷. Metabolomics results show improved energy and anti-oxidant status of RBC and reduced stress, and production of those agents associated with adverse events¹¹. Hemanext technology may potentially improve outcomes for those patients dependent on RBC transfusions to survive by improving the following:

- Reducing transfusion volume
- Increasing transfusion interval
- Increasing hemoglobin increment
- Improving oxygen delivery
- Reducing iron overload
- Reducing sequelae of hemorrhagic shock and transfusion
- Improved quality of life

In summary, based on pre-clinical data, hypoxic red cells have the potential to improve patient outcomes and attenuate transfusion -sequelae. These improvements may be especially effective in patient populations who receive high volumes of RBCs (chronically or acutely). These patients comprise 50% of total RBC usage while only making up 20% of patients transfused^{8,12}.

5.8 Anticipated risks

5.8.1.1 Risks associated with the use of Hemanext ONE system

The current risk management report RMR-001 for the HEMANEXT ONE product concludes that all risks have been reduced as far as possible and no additional residual risks were identified requiring additional clinical evaluation. The documentation demonstrates that the potential benefits outweigh all residual risks.

As part of red blood cell processing and storage there are known risks which may include, but are not limited to risks related to biocompatibility, leak leading to biohazard exposure and or loss of sterility, exposure to endotoxin, hemolysis of red blood cells, and exposure of blood to non-biocompatible materials.

Based on the analysis of the benefit / risk assessment the documentation in RMR-001 supports the following conclusion:

The Hemanext ONE System was demonstrated to be substantially equivalent to commercial red cell products and to meet all requirements for red blood cell manufacture. Through product verification, in vitro, in vivo, and animal studies, the system has shown improved metrics for blood quality.

The potential clinical benefit(s) will need to be demonstrated in patients. The risks also remain equivalent to currently commercially available RBC.

5.8.1.2 Risks associated with RBCs transfusions (Non-exhaustive):

Transfusion of hypoxic RBCs has equivalent risk as transfusion of conventional RBCs, such as³⁸:

- Transfusion-associated graft versus host disease
- Transfusion-related acute lung injury (TRALI)
- Post transfusion purpura
- Transfusion-associated circulatory overload (TACO)
- Transfusion-transmitted infection (TTI)
- Allergic reaction
- Transfusion-associated dyspnea (TAD)
- Febrile non-hemolytic transfusion reaction (FNHTR)
- Hypotensive transfusion reaction
- Delayed hemolytic transfusion reaction (DHTR)
- Delayed serologic transfusion reaction (DSTR)
- Acute hemolytic transfusion reaction (AHTR)
- Major cardiac event (MCE)
- Haematoma (bruise)
- Arterial puncture
- Delayed bleeding (re-bleeding)
- Nerve injury/irritation
- Localized infection/inflammation
- Deep venous thrombosis (DVT)
- Arteriovenous fistula
- Compartment syndrome
- Brachial artery pseudoaneurysm
- Vasovagal reactions

5.9 Justification of the choice of the investigation population

See sections 5.1.4, 5.1.5, and 5.1.6.

6. CLINICAL INVESTIGATION OBJECTIVES

6.1 Overall Objective

The overall objective of this study is to collect preliminary safety data on the transfusion of hypoxic RBCs, manufactured with Hemanext ONE device, in patients with burns and patients with hematological malignancies.

6.2 Primary Objective

Primary Objective – for both patients groups

Hypoxic RBCs safety and tolerance assessment up to 24 hours following the transfusion initiation and overall up to 7 days (+/- 1 day) after the transfusion episode (single transfusion course).

6.3 Secondary Objectives

Secondary Objectives :

- A. For both patients groups
 - 1. Assessment of pre and post transfusion hemoglobin levels
 - 2. Assessment of hemoglobin level before the following transfusion, if applicable
 - 3. Assessment of AEs occurence:
 - i. Up to 7 days (+/- 1 day) post transfusion, in comparison with historical control (including but not limited to infection, deep vein thrombosis, acute respiratory distress syndrome, transfusion-related acute lung injury, transfusion associated circulatory overload, anaphylactic shock, acute haemolytic transfusion reaction).
 - ii. Up to the following tranfusion episode or up to 28 days (+/- 1 day) after the initial transfusion, whichever comes first.
 - From enrollment, up to their subsequent transfusion or 28 days (+/- 1 day) posttransfusion, whichever comes first, through the assessment of patient's diary
 - 4. Assessment of the vital signs during and up to 15 minutes after the transfusion
- B. For burn patients group only:
 - 1. Assessment of arterial blood gases:
 - i. pre-operative
 - ii. intra-operative
 - iii. post operative

6.4 Safety Objectives

All safety objectives are addressed in the primary and secondary objectives.

7. CLINICAL INVESTIGATION OUTCOMES

7.1 Primary Outcome

Primary Outcome – for both patients groups

Number of participants who experienced an adverse event (all types/grades) within a time frame up to 24 hours following the transfusion and overall up to 7 days (+/- 1 day) after the transfusion.

The type and the grade of each adverse event will be categorized according to:

- Association for the Advancement of Blood and Biotherapies (AABB) technical manual, 20th edition (2020)
- Biomedical Excellence for Safer Transfusion (BEST) Collaborative review Lancet 2016; 388: 2825–36
- Local AEs database (for reference)
- ISO 14155-2020 definitions

7.2 Secondary Outcomes

Secondary Outcomes : - for both patients groups

- 1. Evolution of the hemoglobin level before and after the transfusion.
- 2. Hemoglobin increment from transfusion corrected for patient blood volume and hemoglobin dose
- 3. Hemoglobin level before the following transfusion
- 4. Evaluate the frequency of all AEs, including transfusion related AEs up to 7 days (+/- 1) posttransfusion compared to historical data of patient registries (ex. The National Burn Registry)
- 5. Evaluate AEs up to 28 days after the initial transfusion, whichever comes first.
- 6. Evaluation the frequency of all AEs, from enrollment, up to 7 days (+/- 1 day) post transfusion, through the assessment of patient's diary, when applicable.
- 7. Evaluation of patient's vital signs over the course of the transfusion and up to 15 minutes posttransfusion

7.3 Other Outcomes of Interest

Not applicable.

7.4 Safety Outcomes

All safety outcomes are addressed in the primary and secondary outcomes.

8. CLINICAL INVESTIGATION DESIGN

8.1 General clinical investigation design and justification of design

This clinical investigation will be the first use of hypoxic blood manufactured with the Hemanext ONE device and is designed as a safety trial to detect any safety issues related to the hypoxic RBCs.. Subjects will receive two units of hypoxic RBCs.

8.2 Methods for minimising bias

Not applicable. This clinical investigation does not include a comparator.

8.2.1 Randomisation

Not applicable. This clinical investigation does not include a comparator.

8.2.2 Blinding procedures

Not applicable. This clinical investigation does not include a comparator.

8.2.3 Other methods for minimising bias

Not applicable. This clinical investigation does not include a comparator.

8.3 **Unblinding Procedures (Code break)**

Not applicable. This clinical investigation does not include a comparator.

CLINICAL INVESTIGATION POPULATION 9.

9.1 **Eligibility criteria**

9.1.1 **Inclusion Criteria**

- A. Hematological malignancies patients group:
 - 1. Patients > 18 years of age
 - Patients expected to require > 2 unit of red blood cells in a single transfusion event

 - 5. Diagnosis of leukemia, myelomatosis or MDS requiring chronic transfusions
- B. Burn patients group:
 - 1. Patients > 18 years of age
 - 2. Patients who have the capacity to consent by themselves to participate to the clinical investigation
 - 3. Smaller burn patients, hospitalized with a Total Body Surface Area (TBSA%) burn ≥ 10% less and \leq than 50%
 - 4. Patients expected to require \geq 2 unit of red blood cells in a single transfusion event

9.1.2 Exclusion Criteria – both patients groups

- 1. Patients with positive antibody screen
- 2. Patients who do not have the capacity to consent by themselves to participate to the clinical investigation
- 3. Patients with a known hemolytic anemia (congenital or acquired)
- 4. Patients for whom consent has not been obtained
- 5. Patients < 18 years old
- 6. Known or suspected pregnancy
- 7. Patients with a history of major transfusion reactions

Burn patients specific:

- 1. Total body surface area (TBSA%) burn more than 50%
- Patients with combined trauma in need of blood transfusions other than the burn

9.2 Recruitment and screening

9.2.1 Hematological Malignancies Group

Participants will be recruited by the investigators from among the patients with hematological malignancies at the site who receive regular transfusions and who meet the inclusion/exclusion criteria. The purpose and procedures of the study will be explained to prospective participants and their written consent obtained prior to their taking part in the study. It will be emphasised to each prospective subject that, should they wish to withdraw from the study at any stage, they are free to do so without prejudicing their clinical care. Potential participants will be given the opportunity to ask any questions they may have on the design of the clinical investigation and what their participate in this clinical investigation. Once a patent has decided that they wish to participate in this clinical investigation they will be asked to sign an informed consent form.

9.2.2 Burn Group

Participants will be recruited by the investigators from among the burn patients at the site who will require transfusions and who meet the inclusion/exclusion criteria. The purpose and procedures of the study will be explained to prospective participants and their written consent obtained prior to their taking part in the study. It will be emphasised to each prospective subject that, should they wish to withdraw from the study at any stage, they are free to do so without prejudicing their clinical care.

Potential participants will be given the opportunity to ask any questions they may have on the design of the clinical investigation and what their participation will entail. Potential participants will be given the opportunity to ask any questions they may have on the design of the clinical investigation and what their participation will entail. Once a patent has decided that they wish to participate in this clinical investigation they will be asked to sign an informed consent form.

9.3 Assignment to investigation groups

Not applicable. There is only one group in this clinical investigation.

9.4 Criteria for withdrawal / discontinuation of subjects

A participant may be discontinued from the study for the following reasons:

- 1. Serious adverse events
- 2. Withdrawal of consent
- 3. Investigator decision
- 4. Death, any cause

Any participant that enrolled in the study can withdraw from the study, effectively withdrawing consent, at any time, for any reason, without prejudice or consequence. Participants are to be informed that they are free to leave the study at any time for any reason without prejudice or consequence in the informed consent document. If a participant withdraws from the study the data collected up through the time of withdrawal (including testing results) will be included within the study database. Withdrawn participants will be replaced in order to meet the sample size requirements of the study.

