10. CLINICAL INVESTIGATION INTERVENTION

10.1 Identity of the medical device under investigation

All patients will receive one transfusion episode of at least two units of hypoxic RBCs that were manufactured with Hemanext ONE system.

See section 5.2 for details on the Hemanext ONE system. PRO-CLIN-0012 Rev. AB – 16-MAR-2023

See sections 11.1.1 and 11.1.2 for a detailed list of all information being collected.

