11.3.6 Final Follow-Up

This visit will occur at the patient's subsequent transfusion visit or 28 days (+/- 1 day) after their transfusion, whichever comes first. All data from this visit will be collected from the patient's chart. The following data will be collected:

- Adverse event occurrence
- Physical examination
- Concomitant medications
- Pre-transfusion hemoglobin (if applicable)

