12.2 Documentation and reporting in Medical Device clinical investigations

Device deficiencies and all **adverse events (AE)** including all **serious adverse events (SAE)** are collected, fully investigated and documented in the source document and appropriate CRF during the entire investigation period, i.e. from patient's informed consent until the last CIP-specific procedure, including a safety follow-up period.

- Documentation of AEs (including SAEs) by the PI includes diagnosis or symptoms, start and stop dates of event, event treatment, event resolution, assessment of seriousness and causal relationship to MD and/or investigation procedure (ISO14155).
- Documentation of DDs by the PI includes description of event, start date, investigational device information, action taken with regard to the investigational device, and whether the DD led to an AE. The Sponsor shall review all DDs and determine and document in writing whether they could have led to a SAE (DD with SADE potential) (ISO14155).

The Sponsor provides the CEC with the documentation at their request

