7.8 Safety Evaluation

7.8.1 Adverse Events

An overview of all adverse events for both patient groups will be presented, including the number and percentage of patients with at least one, and the total number, of the following:

- Adverse Event (AE) overall up to 7 days (+/- 1 day) after the transfusion.
- Adverse Event (AE) (all types/grades) within a time frame up to 24 hours following the transfusion.
- Adverse event from enrolment up to 7 days (+/- 1 day) following the transfusion
- Adverse event overall
- Serious Adverse Event (SAE)
- Any adverse event leading to withdrawal of the study treatment.
- Adverse Event broken down by relationship to the medical device (Not related, Possible, Probable, Causal relationship).
- Adverse Event broken down by relationship to the study procedure (Not related, Possible, Probable, Causal relationship)
- Adverse Event broken down by severity (Catastrophic, Critical, Serious, Minor, Negligible).
- Any other medication or treatment given because of the occurrence of the adverse event.
- AE broken down by outcome (Fatal, Not recovered/not resolved, Recovered/resolved, Recovered/resolved with sequelae), Recovering/resolving, Unknown).

The incidence of adverse events will be presented by system organ class and preferred term. For each system organ class and preferred term, the total number of adverse events as well as the number and percentage of patient s with at least one adverse event in that system organ class or preferred term will be presented. The incidence of serious adverse events will be presented in the same way.

Separate tables for the incidence of adverse events broken down by severity and the incidence of adverse events broken down by causality assessment (to medical device as well as to study procedure) will also be presented by system organ class and preferred term.

All AEs recorded in the study will be presented in listings.

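### Section 9.4 lets a participant leave the study because of a serious adverse event; once the single transfusion has been given this can cut short only observation, in patients who came to harm

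*Protocol*

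**What the plan says.** Protocol section 9.4 opens with "A participant may be discontinued from the study for the following reasons" and lists four reasons: "Serious adverse events", withdrawal of consent, investigator decision, and death. The object is the study, not the treatment. On what enters the database, the same section adds: "If a participant withdraws from the study the data collected up through the time of withdrawal (including testing results) will be included within the study".

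Section 10.1 fixes the exposure: "All patients will receive one transfusion episode of at least two units of hypoxic RBCs". After that come telephone contacts at 24 hours and at day 7 (11.3.4, 11.3.5) and a final assessment taken from the chart (11.3.6): "This visit will occur at the patient's subsequent transfusion visit or 28 days (+/- 1 day) after their transfusion, whichever comes first".

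Adverse events are to be collected "from patient's informed consent until the last CIP-specific procedure, including a safety follow-up period" (section 12.2). That section also asks for stop date and resolution for every adverse event, related or not.

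The primary outcome is the "Number of participants who experienced an adverse event (all types/grades) within a time frame up to 24 hours following the transfusion", and likewise to day 7. SAP 7.8.1 adds event totals, outcome categories and a row for "Any adverse event leading to withdrawal of the study treatment".

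**The concern.** This is a safety study. When an intervention is given once, a reason for discontinuation that would normally protect the patient from further exposure has nothing left to protect against after the transfusion ends. What it can still end is the telephone calls and the chart review. Because the trigger is a serious event, any loss falls on the patients whose later course matters most.

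At stake are further adverse events in the same patient (including the delayed haemolytic and delayed serologic reactions that section 12.3 lists as expected), the final outcome of the serious event, the adverse event outcome to day 28, and the Visit 5 haemoglobin and physical examination. The data monitoring committee reviews five haematology patients before the remaining patients are enrolled; one truncated record there would be 1/5 = 20% of what it sees.

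**Working it through.** The plan gives no figure to reproduce: the sample size of 20 has no statistical basis, and no serious adverse event rate is stated. The check is of the text, with some simple arithmetic for scale.

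**Does other text keep a discontinued participant under observation?**

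- *Protocol 13.5*: investigators will try to reach transfused patients who dropped out and ask about adverse events, first in the 7-day window and then to the earlier of the next transfusion and day 28. This is an attempt, it concerns adverse events only (not the Visit 5 haemoglobin or examination), and it speaks of patients who dropped out.
- *Protocol 10.4*: the investigator must seek contact with a withdrawn participant to learn the state of health, but the CRF is completed only to the last visit.
- *Protocol 12.2 (repeated in 12.6)*: resolution is to be documented for all adverse events. How this is done for someone no longer in the study is not said.
- *Protocol 12.5*: written follow-up reports are required for serious events related to the device or procedure. An unrelated serious event is not covered.
- *Protocol 11.2.5, 13.4.1 and SAP 7.2.1*: recording or analysis of withdrawn patients stops at the last visit.

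So contact is intended, but no section names discontinuation for a serious event, and no section says that what is learned afterwards enters the CRF or the tables.

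**Follow-up at risk.** With the serious event and discontinuation d days after transfusion, and no earlier transfusion, the days lost are 28 − d:

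- d = 1: 27/28 = 96%
- d = 2: 26/28 = 93%
- d = 3: 25/28 = 89%
- d = 7: 21/28 = 75%

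These are maxima. If the next transfusion falls on day 7 (assumed; section 5.1.5 mentions roughly weekly intervals in intensive treatment), a patient discontinued on day 2 loses 7 − 2 = 5 days. Section 5.5 also ends adverse event collection at discharge for burn patients, which would shorten the period further.

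**Effect on the counts.**

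- Patients with any adverse event: a patient whose serious event began after the transfusion started is already counted, so the change is 1 − 1 = 0. This holds for the primary windows and for the 28-day count.
- Event totals, and patient counts by preferred term: later events can be missed, and none can be added.
- Outcome rows: an event cut off early would probably be entered as not resolved or unknown.

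**How often the rule might be available.** The chance of at least one serious event among 20 patients is 1 − (1 − p)^20. The documents give no p; for assumed values:

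- p = 1%: 18%
- p = 5%: 64%
- p = 10%: 88%
- p = 20%: 99%

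This is the chance that the criterion could be invoked, not that it would be. One affected patient is 1/10 = 10% of a group and 1/20 = 5% of the trial.

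**The case against.** The strongest reply is that the plan already follows people who leave. Section 13.5 reaches to day 28, section 10.4 obliges the investigator to seek contact, and section 12.2 wants resolution for every event. All serious events go to the sponsor within 24 hours, the committee adjudicates all adverse events, and Visit 5 is a chart review, so the source data may well exist. The rule is also permissive (*may*). And because adverse events are collected from consent, a serious event can occur before or during the transfusion, when there is still something to stop. All of this stands, and it limits the point. It does not close the gap between data that exist and data that may be recorded and analysed.

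A reader might go further and infer that section 9.4 ends follow-up for everyone with a serious event, that it biases the primary outcome, or that it makes the outcome tables look safer. The documents do not support these readings. Discontinuation is optional and contact is planned. A patient already counted stays counted. The SAP's outcome categories include not recovered and unknown, so a truncated event would not appear as a good outcome. A reader might also want investigator decision struck from the list, but the harm described here comes from tying departure to a serious event and gives no basis for that.

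SAP 7.3 already tabulates withdrawal from the study with its main reason, and SAP 7.8.1 has a row for events leading to withdrawal of treatment. The SAP thus presupposes a distinction that section 9.4 does not draw.

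**Conclusion.** The point holds in limited form. As written, the protocol permits a transfused participant to be taken off study because of a serious adverse event, and several sections then stop the record or the analysis at the last visit. Later adverse events, the final outcome of the serious event and the Visit 5 data can be lost selectively in harmed patients. Totals of events and patient counts by event type can only be too low as a result; the outcome rows become less informative, in no fixed direction; the number of patients with any adverse event is unaffected.

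The follow-up lost is at most about 26 of 28 days for a serious event on day 2, assuming immediate discontinuation, no earlier transfusion and no successful later contact that is recorded. How often this would happen cannot be derived from the documents. It is worth correcting because the trial's purpose is safety and each patient is 5% of it.

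**What to change.** - *Protocol 9.4*: state that once the transfusion has started a serious adverse event is not by itself a reason to leave the study, and that such a participant stays in the scheduled follow-up through Visit 5 unless consent is withdrawn.
- *Protocol 10.4, 11.2.5, 13.4.1 and SAP 7.2.1*: state that data obtained after discontinuation, including through the contact in 13.5, are recorded in the CRF and analysed.
- *SAP 7.3*: tabulate transfusion stopped separately from left the study.

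Clinical decisions on stopping a transfusion are untouched, and investigator decision remains a listed reason. The cost is a few sentences in a protocol amendment, matching SAP text and one disposition row. No visit is added, because Visits 3 to 5 are already scheduled.
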